Appendix C (The IRB-approved Protocol)

SHEDS-Multimedia); however, few model evaluations have been conducted for other chemical types. These models need to be evaluated for consumer product active ingredients because of their prevalence in the indoor environment and potential asthma morbidity in young children from potential exposures. Biomarker measurements will be collected in order to evaluate objective 6. Results from objective 2 will be employed to assist in these analyses.

To accomplish objective 7 we will evaluate a novel method for rapidly characterizing consumer product inventories in the residential environment. We hypothesize that pictures can be used to adequately capture information on consumer products being used in the home. The results from this effort will then be used to predict exposures to chemicals.

There is a lack of current information on children's activities, locations, and dietary habits, and objective 8 will generate such information. We hypothesize that children's activities, locations, and dietary habits are dependent on age, lifestage, and factors related to their home and community. In combination with multimedia measurements being collected in the Green Housing Study, results from this objective will be used to estimate aggregate and cumulative exposures.

Results from objective 9 will be used for the DNA analysis of mold from dust and measurements of the ERMI values at each time point. We hypothesize that the electrostatic dust collection method is adequate to collect enough dust for DNA analysis. From these electrostatically collected molds, DNA will be extracted and analyzed using HTS analysis. HTS technologies provide the opportunity to holistically explore and identify diverse indoor fungal populations. In addition, the metagenomic data generated from the DNA of dust samples will be used to identify genes and functions that are overrepresented among the fungal biota.

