Appendix C (The IRB-approved Protocol)

2.3 Sample Size Considerations

The sample size for the EPA pilot study add-on is fixed and dependent on CDC's grantee's ability to recruit and retain participants. Using available chemical concentration data for limonene (Sarigiannis et al., 2011), we can estimate the effect sizes we can see given various sample sizes (assumptions: design effect = 2.0, statistical power = 0.8, alpha level = 0.05, correlation = 0.3).

Example: Limonene in air ($\mu\text{g}/\text{m}^3$)

If non-renovated homes have a mean concentration and standard deviation = $15.0 \pm 19.4 \mu\text{g}/\text{m}^3$, with a fixed sample size of $n=35$ participants in each group (renovated and non-renovated homes), we could see a minimum size difference of $11.9 \mu\text{g}/\text{m}^3$.

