3.2 Study Location

The third study site will be determined by CDC based on site selection criteria detailed in their funding opportunity announcement. In the Green Housing Study third study site, the target sample size is 32 green renovated homes and 32 comparison homes. The target sample size for the EPA pilot study add-on is the same number of families as are recruited to participate in the Green Housing Study. Thus, n=64 younger siblings (only one sibling per household) will be the maximum number that could be enrolled as part of the EPA pilot study add-on. Participants in each family will include the index child and a sibling of the index child living in the same household, as well as the mother/caregiver. The index child is defined as the child recruited to participate in the Green Housing Study who ranges in age from 7-12 years with a doctor diagnosis of asthma. By including both the index child and a sibling, it is an opportunity to collect exposure information for two children living in the same household, allowing us to explore differences in exposure based on lifestage.

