Molds: The list of fungi (molds) in Table 6 includes, but is not limited to, fungi/molds identified in water-damaged homes. These were identified with culture-independent studies using quantitative PCR (Vesper et al., 2006a, b). The Environmental Relative Mold Index (ERMI) developed from the Vesper et al. (2007) research showed the fungi/molds in Table 6 associated with asthma in water-damaged homes. Previous research has demonstrated that the ERMI values in homes of infants and children are associated with asthma (Reponen et al., 2011, 2012; Vesper et al., 2013). For this study, we will evaluate the ERMI values pre/post-renovation, 6-months, and 12-months post renovation from the settled dust samples. In addition, we hypothesize that evaluating pre- and post-renovation dust samples for fungal DNA analysis with HTS technologies will provide the opportunity to holistically explore and identify more diverse indoor fungal populations. In addition, the metagenomic data generated from the DNA of dust samples will be used to identify genes and functions that are overrepresented among the fungal biota.

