The ERMI values from the renovated homes will be compared to the traditional homes at each time point using regression analysis. Comparisons between the settled dust and EDC dust will be conducted both pre/post renovation and green versus traditional housing using Pearson correlations. For each child, respiratory data (FEV1%) will be evaluated in relationship to the ERMI value in the home using Pearson correlation analysis. Univariate and multivariate regression analyses will be used to explore different stressors as well as the interactions between different stressors.

Mold information will also be incorporated into statistical analyses to explore relationships between ERMI values in the homes at different times with asthma-like symptoms. The differences in concentrations in the dust samples of individual mold species at each time point will be evaluated using the Wilcoxon rank sum test. Corrections for multiple comparisons will be made using the Holms-Bonferroni test. This test will allow us to determine which mold species are significantly reduced by the renovations. Other analyses will compare the type of

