Appendix C (The IRB-approved Protocol)

Table 8. Urinary metabolites of pesticides measured by the CDC's Division of Laboratory Sciences

Compound	Parent Chemical
cis -2,2-(Dichloro)-2-dimethylvinyl cyclopropane carboxylic acid) (cis -DCCA)	Permethrin, cypermethrin, cyfluthrin
4-Fluoro-3-phenoxybenzoic acid (4F3PBA)	Cyfluthrin
Carbofuranphenol (2,3-dihydro-2,2-dimethyl-7-hydroxybenzofuran) (CFP)	Carbofuran, benfuracarb, carbosulfan
2-Isopropoxyphenol (IPP)	Propoxur
2-Isopropyl-4-methyl-6-hydroxypyrimidinol (IMPY)	Diazinon
para -Nitrophenol (PNP)	Parathion, methyl parathion, nitrobenzene
3,5,6-Trichloro-2-pyridinol (TCPy)	Chlorpyrifos

Blood collection: Blood will be collected to assess allergic sensitization (described below). A 10-ml sample (i.e., 2 teaspoons) of venous blood will be collected into 2 tubes (tubes with coagulant for serum collection) by a trained phlebotomist. The tubes will be centrifuged within 2 hours of collection, serum will be aliquoted into sterile microcentrifuge tubes, and then frozen at -80°C until they can be assayed for total and allergen-specific IgE titer.

Allergy testing: Allergen testing will be performed once at baseline following enrollment. We will use immunoCAP method to assess total and allergen-specific (dust mite, cockroach, cat, mouse, tree mix, grass mix, and weed mix) IgE antibodies in serum. Unfortunately, mold extracts used for measuring IgE are very poor (due to batch-to-batch variability), thus we will not be able to assess sensitization to mold.

Pulmonary function testing: Pulmonary function provides an objective outcome for determining improvements in respiratory health status following the intervention to decrease environmental asthma triggers in the home and improve asthma management. Spirometry (pulmonary function testing or PFTs) will be performed in children with a diagnosis of asthma who are 7-12 years of age. Study participants will be weighed and their heights will be measured using a calibrated scale prior to the start of each testing session. Standard spirometric measures, forced vital capacity (FVC), forced expiratory volume in 1 second (FEV₁), the ratio of FEV₁/FVC, forced expiratory flow between 25-75% of vital capacity (FEF_{25-75%}), and peak expiratory flow (PEF), will be recorded for each patient (Hankinson et al., 1999). All children in this age range may not be able to successfully complete the forced expiratory maneuver required for this test, but

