Appendix C (The IRB-approved Protocol)

attempts to test all children in this age range will be made. All PFT studies will be performed at each home visit to assess possible seasonal variation.

We will not conduct lung function tests on asthmatic children who are in distress; we will reschedule the visit. It is our experience that a phone call to the home approximately 1 hour before the scheduled visit serves not only as a reminder that our research assistants will be visiting the home, but also as an opportunity to inquire if the child will be at home and is ready for the tests (such as lung function, blood draw, etc). If during this phone call, the mother/primary caregiver indicates that the child is in respiratory distress, then we will advise her to hang up and attend to her child and if necessary seek medical attention.

The technician who administers the lung function test in the home is not qualified to determine if the child's lung function is impaired; accurate interpretation of test results requires review by a trained pediatric pulmonologist. We expect that it would take at least 2-3 months for the pulmonologist (site-specific) to review the lung function curves (typically done in batches)—by that time the lung function could have changed for that child. Lung function tests done in isolation (and at any given timepoint) without consideration of other clinical parameters are difficult to interpret. Therefore, we will mail the results of each of the lung function tests (as they become available) to the mother/primary caregiver after review by the pulmonologist. The mother/primary caregiver can then share this information (i.e., repeated lung function tests) with the child's healthcare provider who can better interpret the lung function test results within the context of other relevant parameters (such as recent medication use) that would affect the child's overall asthma management. These results will be provided to participating asthmatic children of both the green and comparison homes to avoid potential bias.

Documentation of the participating asthmatic child's primary care provider will occur at the baseline home visit and participants who do not identify a primary care provider will be referred to one in their local area. A participant who contacts study staff with acute health concerns will be referred to his/her primary care provider or the Emergency Department.

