Appendix C (The IRB-approved Protocol)

measurements and health outcomes between the arms, we began by calculating sample sizes based on each of these measures.

Our sample calculations for environmental measurements (see Table 21) were based on cockroach allergen data in a repeated measures study of the effect of an integrated pest management (IPM) intervention, which indicate that 13 buildings would be necessary in each of the two arms of the study, assuming that 25 subjects could be recruited for each building, yielding 325 subjects/study arm to provide adequate statistical power for environmental measurements.

Our sample calculations for health outcomes (see Table 22) were based on asthma in children subjected to a multifactorial intervention (i.e., education, mattress covers, IPM, and HEPA filter units) in a repeated measures study. These data indicate that 274 subjects/study arm would be needed to provide adequate statistical power for asthma outcomes.

Therefore, since we desired sufficient power to detect meaningful differences in both 1) environmental measurements and 2) health outcomes, we selected the larger of the two estimates — 325 subjects/study arm — as the minimum sample size (see Figure 7). In addition, we augmented this number in order to account for an anticipated 20 percent loss to follow-up over a one-year period. After rounding up where necessary, this increased the sample size to 416 subjects/study arm, comprising 32 subjects (one subject per apartment) in each of 13 buildings in each study arm. The total sample size for the study across both study arms is 832 subjects. The details of our sample size calculations are listed below and the equations that were used were from a book on longitudinal data analysis by Diggle, Liang, and Zeger (1994).

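### The ERMI–FEV1% relation is assigned a Pearson correlation that names no visit and makes no allowance for up to four repeats per child; a mixed model would use the same data better

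*Protocol*

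**What the plan says.** The analysis is in Protocol Section 5.0, Objective 9: "For each child, respiratory data (FEV1%) will be evaluated in relationship to the ERMI value in the home using Pearson correlation analysis". The sentence gives no visit, no rule for summarising a child's visits and no term for clustering. Elsewhere in the same text, the comparison of ERMI between renovated and traditional homes and the test of individual mold species are both specified by time point. A Holm–Bonferroni correction is attached to the species test only.

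Both variables are repeated:

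- **ERMI.** Section 4.3 (Molds): "we will evaluate the ERMI values pre/post-renovation, 6-months, and 12-months post renovation from the settled dust samples". Section 2.2, on Objective 9, likewise refers to "DNA analysis of mold from dust and measurements of the ERMI values at each time point".
- **FEV1.** Appendix A, Pulmonary function testing: "All PFT studies will be performed at each home visit to assess possible seasonal variation". Table 1 in Section 4.1 marks the test as done at all time points.
- **Who is tested.** Spirometry "will be performed in children with a diagnosis of asthma who are 7-12 years of age", and Table 1 lists the index child only. There is therefore about one child with lung function per home.

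Section 4.4 lists four visit periods: baseline, baseline part 2, 6 months and 12 months. At the site "the target sample size is 32 green renovated homes and 32 comparison homes".

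**The concern.** The reference distribution of a Pearson coefficient assumes independent pairs. Up to four pairs from one child in one home are unlikely to be independent: a home tends to keep its mold level and a child tends to keep his or her lung function. The protocol names a method for this relation without saying how the four pairs enter it.

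What is at stake is the use made of a longitudinal design. The study measures each home before and after renovation, so it can ask whether a child's FEV1% moves when the ERMI of that home moves. It can also ask whether children in moldier homes have lower FEV1%. These are different questions, and the second is more open to confounding by whatever else differs between homes. A simple correlation does not separate them. Section 1.3 cites earlier New Orleans work in which higher ERMI went with poorer lung function, so a chance association here could easily be read as confirmation.

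**Working it through.** The protocol gives no sample size, power or error rate for this correlation, so there is no stated figure to reproduce. The check asks how a Pearson test behaves under each way the repeats could be used when ERMI and FEV1% are truly unrelated.

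**Inputs**

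- N = 32 + 32 = 64 children and homes (Section 3.2).
- k = 4 visits (Section 4.4).
- Appendix A, B.1 expects "an anticipated 20 percent loss to follow-up over a one-year period", so 64 × 0.8 ≈ 51 children is also run.
- Alpha is taken as two-sided 5%. This is an assumption, because no level or sidedness is stated for this test.
- The within-home ICC of ERMI and the within-child ICC of FEV1% are **not in the documents**. They are assumed exchangeable, from 0.3 to 0.8 each.
- Two correlations given for other analytes serve as reference points. The limonene example in Section 2.3 lists "alpha level = 0.05, correlation = 0.3", and Appendix A, B.1 gives about 0.5 between successive cockroach allergen measurements. Section 2.3 does not say what its 0.3 refers to. Read as a correlation of repeats in Equation 1 of Appendix A, with design effect 2, 35 per group, SD 19.4, three repeats and one-sided alpha 0.05, it gives 11.91 against the stated 11.9, so that reading is plausible.

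**One value per child (a single visit or the child's mean).** Simulated rejection is 5.0% at ICCs 0.5/0.5 and at 0.8/0.8 with N = 64. The test is valid. A single visit uses 64 of 256 possible pairs. A child mean uses all visits but removes the within-home contrast.

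**Four separate visit-level tests.** Each holds 5%. The chance that at least one is significant is 17.6% at ICCs 0.5/0.5 and 13.9% at 0.8/0.8. Four independent tests would give 1 − 0.95⁴ = 18.5%.

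**All four visits pooled as independent pairs (a conditional case).** The null variance of r is inflated by

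VIF = 1 + (k − 1) × ICC_ERMI × ICC_FEV1,

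and the rejection rate is 2 × [1 − Φ(1.96/√VIF)]. For 0.3/0.3, VIF = 1 + 3 × 0.09 = 1.27, 1.96/√1.27 = 1.74, and the rate is 8.2%. Simulation used 20,000 runs per setting.

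| ICC ERMI / FEV1% | VIF | Formula | Simulated, N = 64 | Simulated, N = 51 |
|---|---|---|---|---|
| 0.3 / 0.3 | 1.27 | 8.2% | 8.4% | 8.3% |
| 0.3 / 0.5 | 1.45 | 10.4% | 10.2% | 10.1% |
| 0.5 / 0.5 | 1.75 | 13.8% | 14.1% | 13.8% |
| 0.5 / 0.8 | 2.20 | 18.6% | 18.7% | 18.5% |
| 0.7 / 0.8 | 2.68 | 23.1% | 23.6% | 23.7% |
| 0.8 / 0.8 | 2.92 | 25.1% | 26.1% | 25.1% |

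At the correlations the documents give for other analytes, pooling would give about 8% (0.3 for both) or 14% (0.5 for both). With fewer usable visits the inflation is smaller. From ICCs 0.5/0.5 to 0.8/0.8 it is 10.7–19.6% with three visits pooled and 7.8–12.9% with two.

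**The case against.** The strongest reply is that the plan does not describe pooling. The sentence takes the child as the unit and speaks of a single value for the home, and Section 5.0 opens by saying that analyses will be done by study time point. On that reading each test holds its 5%. Which visit is used is a detail often left to a statistical analysis plan, which is not shown here. The objective is secondary, no alpha or decision rule is attached to the correlation, and the protocol says that Objective 9 should help inform sampling and sample size at later sites.

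Most of this stands. A reader might infer three stronger things that the documents do not support:

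- *That the planned test has an error rate of 8–26%.* This needs pooling, which is not stated, and ICCs, which are not given.
- *That this is the only planned analysis of mold and lung function.* It is the only named test of ERMI against FEV1%. Objective 9 also plans regressions on stressors, and Appendix A plans regressions of exposures, including mold, on health outcomes.
- *That a separate four-point correlation is intended for each child.* Nothing in the text proposes this.

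The reply does not remove the point about method. The choice of Pearson correlation is made in the protocol. The opening of Section 5.0 also promises longitudinal analyses, so it does not settle the unit here. None of the Pearson readings is both valid and a full use of the repeated data.

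**Conclusion.** The point holds as a recommendation to improve a stated method. The protocol names a correlation for two variables that it measures up to four times on the same child and home, and gives no visit or allowance for repeats. The valid readings either forgo within-home information or produce four tests with no stated correction. That no error rate is demonstrated limits the weight of the point: the multiplicity figure depends on all four visits being tested separately, and the pooling figures depend on an analysis the protocol does not describe and on assumed, exchangeable ICCs.

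The authors already use suitable tools elsewhere. Section 5.0 names general linear and/or mixed models for biomarkers before and after renovation (under Objective 6) and distinguishes within-participant from between-participant correlations (Objective 5). Objective 9 could follow the same approach.

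**What to change.** In Section 5.0, Objective 9, replace the Pearson test with a linear mixed model for FEV1% that has a child random intercept and a visit effect. The visit effect absorbs the seasonal variation that repeated spirometry is meant to capture. Enter ERMI as two terms: the home's mean over its visits (between homes) and each visit's deviation from that mean (within home). Report both slopes with confidence intervals. Pearson coefficients, if wanted, can stay as a description visit by visit, labelled as such and without an inferential claim.

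The cost is a change of wording and slightly more analysis work on the same data. The within-home slope will have only modest precision with about 64 homes, and its confidence interval will show this.

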Appendix C (The IRB-approved Protocol)

mold with presence/absence of asthma-like symptoms. This work will help inform sampling and sample size considerations in future study sites for the Green Housing Study and other studies.

Objective 10: Evaluate the feasibility of using a simplified mass balance approach to estimate chemical exposure and dose rates incorporating children's toenail clippings, other multimedia measurements, and activity information

The collection of toenail clippings is attractive because obtaining the sample is noninvasive and easily performed by the primary caregiver. Arsenic, cadmium, mercury, manganese, zinc and other elements may be sequestered in toenails and hair following environmental exposures and have utility in determining exposure and dose rates and serve as simple, low cost metrics to supplant other biomarkers, such as blood or urine, particularly for children. This objective will evaluate the relationship of toenail clippings with other environmental and biological measures and determine the feasibility of using toenail clippings to estimate chemical exposure and dose rates for very young children in observational exposure measurement studies. Associations and correlations between renovation activities, sources, exposure pathways, and indoor/outdoor concentrations will be evaluated. Descriptive, univariate and multivariate analyses will be conducted. Correlations (both Spearman and Pearson), linear regression modeling, and F-tests and t-tests will be conducted in order to evaluate relationships both within and between the measurement data to elucidate relationships and associations.

Objective 11: Examine the feasibility of obtaining extant community-level data and prepare draft approaches for using such data for children's community exposure factor assessment and multiple stressors effects on estimates of health risks

Environmental factors affecting children's health may not be limited to those in their immediate indoor residential space. Children may be exposed to environmental contaminants that originate elsewhere in their community. In addition, there may be non-chemical community-level stressors that result in joint effects with chemical stressors. For example, residential proximity to road traffic has been associated with asthma occurrence and exacerbations (Salam et al., 2008). Exposure to traffic pollutants may be mediated not only by children's activities, but also residential conditions. Other community factors, including community violence (Sternthal et al., 2010) and socio-environmental factors (Gupta et al., 2009) have been found to be associated with differences in asthma risk. Research is needed to better understand whether and how chemical exposures may interact with non-chemical stressors. Two approaches will be used to examine community-level effects or interactions. First, information will be collected about several aspects of the children's time, activity, and location with regard to their community and how it relates to their chemical exposures and health outcomes. Second, geospatial information will be used to examine several community-level domains for which extant data may be available in the city selected for the main study. These domains may include pollutant concentrations, pollutant sources, health, built environment, land use, neighborhood socio-economic status, crime, employment, education, food availability, and possibly other metrics where extant data suitable for geospatial analyses are available. When applied to only a single housing location, analyses will be limited to examining associations between children's interactions with the community and the child's biomarker and health measures. When applied to multiple housing locations,

